2.2 Design

A mixed experimental design of 2 (Stimulation type: anodal stimulation, sham stimulation) \times 2 (Learning strategy: retrieval practice, restudy) \times 2 (Retention interval: Immediate recall, Delayed recall) was employed. Stimulation type was a between-subjects variable, while learning strategy and testing time were within-subject variables. The dependent variables were the correct recall rate and Adjusted Ratio of Clustering (ARC) scores in the testing phase.

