2.4 Procedure

Treatment was administered by two examiners, and after a total of 10 sessions over 5 consecutive days, a final group of 52 patients participated in the learning and testing phase. Among them, 27 received anodal stimulation, while 25 received sham stimulation. Each participant of each stimulation type was involved in both learning conditions, meaning that all participants completed both retrieval and restudy learning and testing (experimental procedure in **Figure 1**).

(1) Stimulation phase

In the anodal group, the anode was placed over the left DLPFC (F3), and the cathode was placed over the contralateral supraorbital area (FP2). A direct current of 2mA was applied for 20 minutes during each stimulation session. Stimulation was conducted twice a day, at 9 a.m. and 2 p.m., for 5 consecutive days, totaling 10 sessions. In the sham group, the stimulation parameters, including the stimulation site and duration, were identical to those of the anodal group. However, during the 10-second ramp-up and ramp-down periods before and after stimulation, patients were unaware that the current was turned off.

(2) Learning phase

The experimental procedure followed the classic retrieval practice paradigm, which included a learning phase and a final test phase.

During the experiment, participants were informed that they would learn two lists of words. Subsequently, they might either learn the words again or complete a list recall test, and will be given a final test shortly thereafter. The learning of the retrieval practice list and the restudy list was conducted in a randomly balanced manner. Each word was presented for 5 seconds, with a 500-millisecond interval between words. To avoid providing secondary retrieval cues between examples, all words were shuffled pseudo-randomly within categories. Each list contained 17 words, consisting of 5 examples from each of the 3 experimental categories (15 experimental examples, 2 filler examples). The first and last words presented in each list were filler words, thus controlling for the primacy and recency effects on memory.

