2.5 Date scoring & analysis

The experimental results were processed using SPSS 26.0. The correct recall rate of word lists was calculated for each subject by the experimental assistant. Then, Free recall organization was measured by the Adjusted Ratio of Clustering (ARC) scores [14,15]. ARC scores range from 1 to 1. A 0 score indicates a level of clustering similar to what would be expected by chance, and a score of 1 implies perfect clustering. Negative values of ARC scores mean atypical and uninterpretable recall patterns[16]. For that reason, negative scores were excluded from analyses.

A mixed-design analysis of variance (ANOVA) was conducted to compare the correct recall rates and ARC clustering scores between the two learning strategies under two stimulation conditions. All statistical tests were performed at a significance level of 0.05, and post-hoc comparisons were adjusted using Bonferroni correction. Effect sizes were reported using partial eta-squared (η_p^2 ; ANOVAs).

3. Study Status

Record Verification: July 2024

Overall Status: Completed

Study Start: July 24, 2023 [Actual]

Primary Completion: January 30, 2024 [Actual]

Study Completion: April 15, 2024 [Actual]

List of abbreviations

tDCS transcranial direct current stimulation

L-DLPFC left dorsolateral prefrontal cortex

VLPFC ventrolateral prefrontal cortex

ARC Adjusted Ratio of Clustering

References

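### The word-shuffling rule, read literally, gives category-blocked lists; that defeats its stated purpose and confounds ARC with memory for presentation order

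*Protocol*

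**What the plan says.** Section 2.4, under the learning phase, gives the ordering rule, "all words were shuffled pseudo-randomly within categories", and in the same sentence its reason: "To avoid providing secondary retrieval cues between examples". The same paragraph sets the list at 17 words, made up of three experimental categories of five words and two fillers. It adds that "The first and last words presented in each list were filler words", so no filler separates the experimental words. No rule is given on whether words of one category may be neighbours, or on whether the order is redrawn for each study cycle.

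Section 2.2 names the outcomes: "The dependent variables were the correct recall rate and Adjusted Ratio of Clustering (ARC) scores in the testing phase". Section 2.5 gives ARC its role, "Free recall organization was measured by the Adjusted Ratio of Clustering (ARC) scores", and its anchors: zero is chance, and "a score of 1 implies perfect clustering". It then drops negative scores from the analysis. The introduction ties this outcome to the study's aim of better semantic organisation.

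**The concern.** Shuffling inside a category changes the order of its five words and leaves the category together. Words of one category then stand side by side, where they can cue each other, and that is what the first half of the sentence says it wants to avoid. The sentence therefore contradicts itself.

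The contradiction matters because ARC counts neighbouring recalled words of the same category. If the input is already grouped by category, a patient who remembers only presentation order produces those neighbours without organising anything by meaning. An effect of stimulation or of learning strategy on ARC could then be an effect on order memory, while the study would report it as semantic organisation.

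**Working it through.** **Inputs from the protocol.** Three categories of five words per list, with fillers only at the ends (Section 2.4); ARC anchored at 0 and 1, with negative scores excluded (Section 2.5).

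**Assumptions.** The protocol does not print the ARC formula. The usual one fits its anchors:

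ARC = (R − E) / (maxR − E), with E = Σnᵢ²/N − 1 and maxR = N − k,

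where R is the number of adjacent same-category pairs in recall, nᵢ the words recalled from category i, N the total recalled and k the number of categories recalled. ARC is taken to be scored per list on the experimental words. Recall level and the share of serial steps are not in the protocol, so they are varied below.

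**Exact serial recall, all 15 words.** E = (25 + 25 + 25)/15 − 1 = 4 and maxR = 15 − 3 = 12.

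- Blocked list: R = 12, so ARC = (12 − 4)/(12 − 4) = 1.00.
- List with no same-category neighbours: R = 0, so ARC = (0 − 4)/(12 − 4) = −0.50.
- List mixed at random across categories: mean ARC about 0.00 (SD 0.21, simulated).
- Recall grouped by category, whatever the list order: ARC = 1.00.

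The blocked result does not need full recall. In serial recall of any subset of a blocked list, each category's words stay together, so R = N − k = maxR. ARC is then 1 whenever it can be computed.

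**Partly serial recall, no semantic clustering.** Simulated recalls in which half of the steps go to the next remembered word in presentation order and the rest are random:

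| Recall | Blocked, all scores | Mixed, all scores | Blocked, negatives excluded | Mixed, negatives excluded | Gap after exclusion |
|---|---|---|---|---|---|
| 40% | 0.24 | 0.00 | 0.57 | 0.49 | 0.08 |
| 60% | 0.30 | 0.00 | 0.43 | 0.27 | 0.16 |
| 80% | 0.34 | 0.00 | 0.40 | 0.20 | 0.20 |

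Repeat runs differ by about 0.01 to 0.02. Another coding of the serial step gives 0.36 in place of 0.30 at 60% recall, so 0.30 is not an upper bound. A different model, in which recall follows presentation position with random jitter (SD 3 positions), gives raw blocked means of 0.14, 0.22, 0.33 and 0.42 at 40%, 60%, 80% and 100% recall. With wholly random recall order the blocked mean is about 0.00.

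**Effect of excluding negative scores.** For mixed lists with no semantic clustering, about half of the recalls score below zero at 40% to 80% recall (47% to 51%), and about 39% do at full recall. At 60% recall, dropping them moves a true mean of 0.00 to about 0.27. The exclusion therefore distorts ARC even when the lists are properly mixed.

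**The case against.** The strongest reply is that blocking is inferred. The protocol never says that categories were blocked. The purpose clause points to mixing across categories, and the phrase may be a slip of drafting or translation. This stands, and it is why the point concerns the rule as written and asks what was done. It does not remove the point: either the sentence is wrong or the outcome is confounded.

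Three stronger readings are tempting, and the documents do not support them.

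- *ARC could not measure organisation at all.* Even under blocking it runs from about 0 for random order to 1 for grouped or strictly serial recall. It is confounded, not void. The task is free recall, with arithmetic between cycles and a second test after 24 hours, so strict serial recall need not be common.
- *The comparison of arms is biased.* Every participant completed both learning conditions, and nothing says that list order differed by arm. Blocking would not by itself create a difference between anodal and sham stimulation. It would leave the meaning of a difference open.
- *The artefact differs by learning strategy.* Study exposures do differ (two study cycles against four, Section 2.4). However, the calculation models a single presentation, and the protocol does not say whether the order was redrawn. Neither the size nor the direction of such a difference is established.

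It is also fair to object that the raw contrast of 0.30 against 0.00 is not the analysed quantity. After the Section 2.5 exclusion the gap is smaller and depends on the recall level, as the table shows. Correct recall rate, the other dependent variable, is not shown to be affected.

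**Conclusion.** The point holds in this form: the ordering rule conflicts with its own purpose, and if it was followed literally, ARC mixes semantic grouping with memory for presentation order. That exact serial recall of a blocked list scores 1.00 follows from the formula alone. The size under partial serial recall rests on assumed behaviour. At 60% recall with half of the steps serial, mean ARC without semantic clustering is about 0.30 against 0.00, or about 0.43 against 0.27 on the scale that Section 2.5 analyses. The analysed gap ranges from 0.08 to 0.20 between 40% and 80% recall. Whether the lists were in fact blocked cannot be settled from the protocol text.

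**What to change.** The rule should read that the 15 experimental words of each list are presented in an order randomised across categories, newly drawn for each study cycle. It should not force neighbours to differ in category: at 60% recall, fully serial recall of such lists has a mean ARC of about −0.28, and most of those scores would be dropped under Section 2.5.

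Section 3 lists the study as completed, so the order can no longer be changed. For this trial:

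1. State the presentation order actually used, any constraint on same-category neighbours, and whether the order was redrawn at each cycle.
2. If the lists were mixed, correct the sentence.
3. If they were blocked, report a measure of serial-order recall beside ARC, or adjust for it, and do not interpret ARC differences as semantic organisation alone. The new wording must not be inserted as a description of what was done.
4. In either case, keep negative ARC scores in the analysis.

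The cost is a little extra scoring of recall order and a more cautious claim. No further patients or sessions are needed. In any reuse of the protocol, the change is one sentence and one setting in the presentation software.

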A study involving 119 healthy subjects investigated the combination of tDCS intervention with retrieval practice and found that the strong retrieval practice effect left no room for tDCS to improve memory performance[7]. The combination of single-session online tDCS with retrieval practice in healthy individuals and found that the memory performance of anodal stimulation was inferior to cathodal stimulation and sham stimulation [8]. We have already explored the role of continuous periodic tDCS combined with interim testing on spatial route learning in patients with schizophrenia in a previous study [9], and found that both the learning strategy and tDCS independently facilitated the ability of patients with schizophrenia to learn new information in spatial route learning, suggesting that the tDCS of L-DLPFC has a significant improvement effect. In contrast, targeted tDCS treatment may be more effective for memory-impaired populations such as schizophrenia [10]. Therefore, further investigation is needed to determine the effectiveness of combining tDCS and retrieval practice for semantic memory intervention in schizophrenia patients. From a theoretical perspective, this combination may have a dual activation effect because (1) tDCS stimulation can enhance activation levels of the L-DLPFC, improving its cognitive function impairment; (2) retrieval practice can not only help patients initiate semantic memory strategies and promote semantic elaboration but also actively activate the brain regions stimulated by tDCS, thereby producing a synergistic effect.

Therefore, this study aims to investigate whether combining tDCS with retrieval practice facilitates the maintenance of semantic memory and improvement of semantic organization by comparing the use of retrieval practice strategies in patients receiving anodal L-DLPFC stimulation, sham stimulation.

2. Methods

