2.3.2 Materials

Thirty-four words from eight common semantic categories were selected as the learning materials. Among them, five words were chosen from each of the six categories (fruits, clothing, musical instruments, sports, stationery, media) as experimental items, while two words were selected from each of the remaining two categories (daily necessities, body organs) as filler items. These filler items were presented at the beginning and end of the learning list to control for primacy and recency effects, respectively.

The selection of experimental categories followed the following rules:(1)To control for the mutual influence between categories, relatively unrelated categories were chosen (the main control was the degree of association between categories and their knowledge domains, such as choosing between fruits and vegetables); (2)Two-character words with clear semantics were selected as sample words. The selection of sample words followed these rules: 1) Each sample word was a two-character word with clear semantics; 2) Each sample word had a different pronunciation [13].

Prior to the formal experiment, 20 schizophrenia patients were randomly selected as participants to assess the semantic familiarity and relevance of 30 pairs of category sample word pairs. Evaluation was conducted on a Likert five-point scale (1 indicating complete

unfamiliarity or no relation, and 5 indicating complete familiarity or very close relation). The results indicated that there were no significant differences between the familiarity ($M = 4.42$, $SD = 0.76$) and relevance ($M = 4.75$, $SD = 0.47$) of the retrieval practice list (fruits, clothing, instruments) and the familiarity ($M = 4.61$, $SD = 0.59$) and relevance ($M = 4.65$, $SD = 0.45$) of the restudy list (sports, stationery, media), $t(19) = -1.765$, $p = .094$, 95% CI [-0.41, 0.03], $t(19) = 1.344$, $p = .195$, 95% CI [-0.05, 0.25].

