For the retrieval practice list, participants underwent two learning sessions and two retrieval sessions (S-T-S-T). During retrieval, participants were instructed to write down all the words they had just remembered within 5 minutes. For the restudy list, participants underwent four study sessions (S-S-S-S). Between each learning cycle, participants completed a 3-minute simple arithmetic task (dispersed attention task).

(3) Testing phase

Immediate Test: Participants were instructed to recall as many words as possible from the learned lists within 10 minutes after completing all learning tasks.

Delayed Test: Participants were informed to recall as many words as possible from the

learned lists within 10 minutes 24 hours later.

[figure not shown]

Figure 1. Experiment procedure.

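### Does the five-minute limit on each practice recall leave time on task uncontrolled between retrieval practice and restudy?

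*Protocol*

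**What the plan says.** All of the relevant text is in the Protocol.

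- **Study pace (section 2.4, Learning phase).** "Each word was presented for 5 seconds, with a 500-millisecond interval between words". Each list has 17 words: 15 experimental and 2 filler.
- **Sessions per list (section 2.4).** The retrieval practice list gets two study and two recall sessions in alternation (S-T-S-T). The restudy list gets four study sessions (S-S-S-S).
- **Recall sessions (section 2.4).** "During retrieval, participants were instructed to write down all the words they had just remembered within 5 minutes". The visible text gives no minimum length and no rule for a patient who finishes early.
- **Interval task (section 2.4).** Three minutes of arithmetic separate the learning cycles. The term cycle is not defined.
- **Aim (end of section 1).** The combination of tDCS and retrieval practice is to be studied by "comparing the use of retrieval practice strategies in patients receiving anodal L-DLPFC stimulation, sham stimulation".
- **Design and analysis (sections 2.2 and 2.5).** Stimulation is between subjects. Strategy and retention interval are within subjects. A mixed ANOVA is applied to recall rate and ARC.

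Section 2.4 refers to Figure 1 for the experimental procedure. The figure is not reproduced in the text available for this review.

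**The concern.** The experimenter paces one list completely, while the patient can partly pace the other. If time spent on a list improves later recall, a difference between retrieval practice and restudy could partly reflect minutes worked rather than the act of retrieving. At the five-minute limit the retrieval list would have more than twice the working time of the restudy list. The strategy main effect in the section 2.5 ANOVA would then be hard to interpret. If patients under anodal stimulation used their recall time differently from sham patients, the interaction would be harder to explain as well. The Protocol takes care over other list properties, such as rated familiarity and relevance, filler words and balanced learning of the two lists, so the absence of any statement on time per list stands out.

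**Working it through.** **Inputs.** From section 2.4: 17 words per list, 5 s per word, 0.5 s between words, the session sequences, and an upper limit of 300 s per recall. The actual recall length *r* is not given. The range 60 to 300 s is used; 60 s is an assumption and only 300 s is documented. The Protocol states no total time per list, so there is no figure of its own to reproduce.

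**Time per list.**

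- Study session: 17 × 5 + 16 × 0.5 = 93 s.
- Restudy list: 4 × 93 = 372 s.
- Retrieval list: 2 × 93 + 2*r* = 186 + 2*r*.

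| Assumed *r* (s) | Retrieval list (s) | Restudy list (s) | Ratio |
|---|---|---|---|
| 60 | 306 | 372 | 0.82 |
| 93 | 372 | 372 | 1.00 |
| 180 | 546 | 372 | 1.47 |
| 300 | 786 | 372 | 2.11 |

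If an interval also follows the last word, a session lasts 17 × 5.5 = 93.5 s, and the extremes become 307 and 787 s against 374 s. Word presentation runs the other way at every *r*: 186 s for retrieval against 372 s for restudy.

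Elapsed time depends on how many arithmetic tasks each list contains. With three per list (540 s), it is 846 to 1326 s for retrieval against 912 s for restudy. With only one on the retrieval list, it is 486 to 966 s.

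So the sign of the working-time difference is not determined: the lists are equal at 93 s per recall, and the retrieval list is shorter below that and longer above it.

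**What this does to each effect.** Let δ be whatever unequal time adds to the retrieval-minus-restudy difference.

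- *Strategy main effect:* contains δ. It describes the retrieval procedure as run.
- *Stimulation main effect:* both arms follow the same procedure, so a common δ contributes equally to each and drops out of anodal minus sham.
- *Interaction:* the strategy difference under anodal minus that under sham contains δ − δ = 0. Something remains only if stimulation changes the recall time used or the benefit drawn from it. The document gives no evidence of either. Learning follows the ten stimulation sessions, so a change of that kind would be a consequence of the allocated stimulation. It would bear on how an interaction is explained, not on whether the arms are comparable.

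**Would a common session length repair it?** With common length *L*, word pace becomes (*L* − 8)/17: 5.0 s at 93 s, 8.35 s at 150 s and 10.12 s at 180 s. At 93 s, recall may be cut short; at the longer lengths, study is slowed. Four study sessions against two leaves word presentation at 2:1 whatever *L* is. Section 2.3.2 also assigns fruits, clothing and instruments to retrieval and sports, stationery and media to restudy, so equal timing alone would not isolate retrieval.

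**The case for a change.** The best case for the concern is that it holds on either reading of the five-minute limit. As a cap, recall is patient-paced on one list only. As a fixed window, the lists take 786 and 372 s. They match only if recalls average 93 s, and nothing in the visible text arranges that. Task timing is procedure and belongs in a protocol rather than in an analysis plan. The aim is a synergy between stimulation and retrieval, so the content of the strategy contrast matters to the reader.

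Part of this stands. The arithmetic is right, the visible text does not equate working time, and the strategy effect cannot be read as retrieval with time held constant. The step from there to a fault in the plan does not follow. Section 2.4 makes no promise of equal time that its own numbers break. What it does fix, four sessions per list, is consistent. Exchanging study for recall necessarily changes both activity and exposure. Knowing whether recalls ended when the patient stopped would be useful detail, but it would alter no planned comparison, and Figure 1 may already supply it.

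**Conclusion.** The concern does not hold. Working time per list is left open in the visible text, within 306 to 786 s against 372 s for recalls of 60 to 300 s. The lower end rests on an assumed 60 s, and the upper end requires both recalls to use the full limit. This shows that time was not matched in the text; it does not establish which list took longer. The Protocol contradicts neither itself nor any figure it states, and matching on number of sessions is a legitimate choice. The stimulation main effect is unaffected provided both arms followed the same procedure, as described. The interaction is unaffected unless stimulation altered recall time or its benefit, which nothing in the document suggests. What remains is a limit on how the strategy effect is interpreted. Because the procedure figure cannot be seen, absent session lengths cannot be counted against the plan.

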2.5 Date scoring & analysis

The experimental results were processed using SPSS 26.0. The correct recall rate of word lists was calculated for each subject by the experimental assistant. Then, Free recall organization was measured by the Adjusted Ratio of Clustering (ARC) scores [14,15]. ARC scores range from 1 to 1. A 0 score indicates a level of clustering similar to what would be expected by chance, and a score of 1 implies perfect clustering. Negative values of ARC scores mean atypical and uninterpretable recall patterns[16]. For that reason, negative scores were excluded from analyses.

A mixed-design analysis of variance (ANOVA) was conducted to compare the correct recall rates and ARC clustering scores between the two learning strategies under two stimulation conditions. All statistical tests were performed at a significance level of 0.05, and post-hoc comparisons were adjusted using Bonferroni correction. Effect sizes were reported using partial eta-squared (η_p^2 ; ANOVAs).

3. Study Status

Record Verification: July 2024

Overall Status: Completed

Study Start: July 24, 2023 [Actual]

Primary Completion: January 30, 2024 [Actual]

Study Completion: April 15, 2024 [Actual]

List of abbreviations

tDCS transcranial direct current stimulation

L-DLPFC left dorsolateral prefrontal cortex

VLPFC ventrolateral prefrontal cortex

ARC Adjusted Ratio of Clustering

References

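### ARC cannot be computed for very short recalls, so the mixed ANOVA in Protocol 2.5 may drop poor rememberers, and the short-recall scores that it keeps are biased upward

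*Protocol*

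**What the plan says.** Protocol 2.2 names two dependent variables, the correct recall rate and ARC, and sets out the factors: "Stimulation type was a between-subjects variable, while learning strategy and testing time were within-subject variables". Each patient therefore has four ARC cells, two strategies by two tests.

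Protocol 2.4 fixes the material: "Each list contained 17 words, consisting of 5 examples from each of the 3 experimental categories". The other two words are fillers, which leaves 15 scorable words per list.

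Protocol 2.5 anchors the measure ("A 0 score indicates a level of clustering similar to what would be expected by chance, and a score of 1 implies perfect clustering") and removes part of its scale ("For that reason, negative scores were excluded from analyses"). It then states the analysis: "A mixed-design analysis of variance (ANOVA) was conducted to compare the correct recall rates and ARC clustering scores". It sets no minimum number of recalled words, and it does not say what happens to a patient whose ARC cannot be computed in one cell. Neither 2.4 nor 2.5 gives an expected or observed recall level.

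**The concern.** ARC rescales the observed clustering between its chance value and its maximum. When few words are recalled these two values are equal, and no score exists. ARC is then missing because recall was poor, and recall is the other outcome that stimulation and learning strategy are meant to change. A standard repeated-measures ANOVA needs all four cells, so a single missing cell takes out all of that patient's data. Selection of this kind can differ between the anodal and sham groups, which undoes part of what randomisation provides.

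A second difficulty concerns the scores that survive. If short recalls score high merely because they are short, a condition that improves recall could appear to worsen organisation. ARC is the protocol's only measure of semantic organisation, and improving that organisation is part of the aim stated at the end of section 1.

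**Working it through.** **Inputs.** From the protocol: 3 categories of 5 scorable words per list (2.4), four cells per patient (2.2), negative scores excluded (2.5), 52 patients (2.4). Assumed: ARC is scored per list without fillers, words are recalled independently within a list, and the recall rate takes a range of values because none is given.

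**Formula.** ARC = (R − E)/(M − E), where R is the number of adjacent same-category pairs, E = Σnᵢ²/N − 1 is its chance expectation, M = N − k is its maximum, N is the number of words recalled, nᵢ the number from category i, and k the number of categories recalled. The protocol does not print the formula. This standard form reproduces its anchors: R = E gives 0 and R = M gives 1.

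**When ARC is undefined (M = E).**
- N = 0: nothing to score.
- N = 1: E = 1/1 − 1 = 0, M = 0.
- N = 2, same category: E = 4/2 − 1 = 1, M = 1. Different categories: E = 2/2 − 1 = 0, M = 0.
- N = 3: undefined for 1+1+1 (5 × 5 × 5 = 125 selections) and for three from one category (3 × 10 = 30), out of 455. That is 155/455 = 34.1%.
- N = 4: four from one category, 15/1365 = 1.1%.
- N = 5: five from one category, 3/3003 = 0.1%.
- N ≥ 6: never.

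**Undefined share per cell.** u = P(N ≤ 2) + 0.341·P(N = 3) + 0.011·P(N = 4) + 0.001·P(N = 5), with N binomial(15, p). At p = 0.40: 0.0271 + 0.341 × 0.0634 + 0.011 × 0.1268 + 0.001 × 0.1859 = 0.050.

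**Patients with at least one undefined cell.** With the same p for everyone this is 1 − (1 − u)⁴. The last column lets p vary between patients (beta distribution, intraclass correlation 0.2, assumed).

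| Mean recall | Undefined per cell, same p | Patients affected, same p | Patients affected, p varies |
|---|---|---|---|
| 0.25 | 32% | 78% (41 of 52) | 67% (35 of 52) |
| 0.30 | 19% | 56% (29) | 58% (30) |
| 0.40 | 5% | 19% (10) | 40% (21) |
| 0.50 | 0.9% | 3.5% (2) | 25% (13) |
| 0.60 | 0.1% | 0.4% (0) | 14% (7) |

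**Retained scores under chance order.** With 2+1 words, E = 5/3 − 1 = 0.667 and M = 1, so ARC is 1 (R = 1) or (0 − 0.667)/0.333 = −2 (R = 0). Once −2 is excluded, every retained 3-word score is exactly 1. Enumerating all recall patterns and orders, then removing negative scores, gives:

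| Words recalled | Mean, all defined scores | Mean, negatives excluded | SD, negatives excluded |
|---|---|---|---|
| 3 | 0 | 1.00 | 0 |
| 4 | 0 | 0.86 | 0.35 |
| 6 | 0 | 0.42 | 0.35 |
| 10 | 0 | 0.25 | 0.19 |
| 15 | 0 | 0.14 | 0.14 |

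Before exclusion the chance mean is 0 at every length. After it, the score of a patient with no organisation at all depends mainly on how many words were recalled.

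**The case against.** The strongest reply is that the protocol does not say that patients were dropped. Undefined scores might have been set to a value, or there may have been none. Two study and two retrieval rounds, or four study rounds, on 15 words could bring recall to 0.60 or more, where the undefined share per cell is about 0.1% if patients are alike. A rule for undefined scores may also stand in a statistical analysis plan that is not shown. All of this stands as a limit on size. It does not remove the point, because the analysis named in 2.5 discards incomplete patients in its usual form, and 2.5 names no alternative.

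A reader might go further in three ways that the documents do not support.

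- One might object to the range sentence, "ARC scores range from 1 to 1". A minus sign was probably lost when the text was extracted. A lower limit of −1 would not be exact either (the minimum is −2 for 2+1 words and −0.5 for 5+5+5), but this has no effect on the analysis: negatives are excluded, so every analysed score lies between 0 and 1. The anchor sentence itself is correct for every defined score.
- One might say that noise from short recalls swamps the precise scores. The chance SD of all defined scores is 1.41 at 3 words and 0.21 at 15, about a 45-fold ratio of variances, but those SDs include the negative scores that 2.5 removes. In the retained scores the SD is 0 at 3 words, and what remains at short lengths is mainly upward bias.
- One might weight each score by the inverse of its chance variance. The weights would depend on recall after treatment and would let good rememberers dominate, which is the same selection in another form.

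**Conclusion.** The point holds, with a size that the protocol does not let anyone fix. That ARC is undefined at two words or fewer, and for one-category or all-singleton recalls of three to five words, is a mathematical fact about this list design. That patients are lost is conditional on complete-case handling. The number could be close to none (recall 0.60 with little variation between patients) or more than half of the 52 (recall 0.30 or below). It would be wrong to state that the poorest rememberers were dropped; the plan as written allows it and does not guard against it.

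The upward bias of short recalls follows from the stated exclusion of negative scores together with the list design, whatever the recall rate. How much it matters again depends on how many short recalls there are. The figures assume independent recall of words, and the bias figures assume chance order. Patients who truly cluster would have fewer negative scores and less bias. The consequence is confined to the ARC comparison; the recall-rate analysis is not affected.

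**What to change.** In 2.5, replace the mixed ANOVA for ARC with a linear mixed model that has the same fixed factors (stimulation, strategy, test and their interactions) and a random patient intercept, fitted to every defined cell instead of complete cases. Say that ARC is undefined when its chance and maximum values coincide. Report the number of undefined scores by arm, strategy and test. Do not weight the main analysis by the number of words recalled.

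The cost is analysis wording and a short script on existing recall sheets. Section 3 lists the study as completed, so the change should be labelled as made after data collection. The model is slightly more complex than the ANOVA, and partial eta-squared gives way to an estimated difference.

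Two limits remain. Undefined cells are not recovered: the model keeps a patient's other cells but cannot supply a score that does not exist, so the counts are essential. Nor does it remove the upward bias of short recalls, which comes from excluding negative scores, so ARC differences should be read beside the recall rates of the same cells.
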